8.7.4 Electrocardiogram

Electrocardiograms will be performed at the time points described in the Schedules of Assessments ([Table 1.3-1](#)) after resting for at least 10 minutes and before blood sampling. Subjects should be monitored for potentially clinically significant ECG results.

The investigator or subinvestigator will record the 12-lead ECG using the 12-lead ECG monitor provided by the central ECG measurement facility and record the date and time of the measurement in the source document and the eCRF. The original 12-lead ECG tracing will be retained in the medical record or investigator file. The central ECG measurement facility will collect the 12-lead ECG data, and measure the heart rate, PR interval, RR interval, QRS interval, QT interval, and QTc interval [$QTcF = QT$ interval/ $(RR\ interval)^{1/3}$] to be judged by physician in the central ECG measurement facility. The central ECG measurement facility will report the analysis results to the investigator or subinvestigator who confirms the results. The report on analysis results will be officially documented by entering the date of confirmation and signing by the investigator or subinvestigator. The investigator or subinvestigator will assess the results with reference to the “Report on Analysis Results” prepared by the central ECG measurement facility and record the results of normal/abnormal assessment and abnormal findings in the source document and the eCRF. The analysis results will be directly reported to the sponsor by the central ECG measurement facility in electronic files. Therefore, it is not necessary to record the results in the source document and the eCRF.

8.7.5 Suicidality Monitoring

Not applicable.

8.7.6 Other Safety Variables

8.7.6.1 Height/body Weight

Body weight and height will be measured at the time points described in the Schedules of Assessments (Table 1.3-1), and the dates and results of measurements will be recorded in the source document and the eCRF (body weight in units of 0.1 kg and height in units of 0.1 cm). Body weight will be measured using a calibrated and reliable scale. The same scale should be used for the same subject as much as possible, and the measurement will be done using the standard method (without shoes and with normal clothing). Height will be measured only at Week -5 (Visit S1). Body mass index {BMI = body weight [kg]/(height [m])²} will be calculated using the body weight measured at Week -5 (Visit S1) to confirm that the subject meets the inclusion criteria.

8.8 Adverse Events

8.8.1 Definitions

An AE is defined as any untoward medical occurrence in a clinical trial subject administered an IMP and which does not necessarily have a causal relationship with this treatment. In this trial, any untoward medical occurrence in a subject not receiving the IMP will be included. Adverse events would not include information recorded as medical history at screening for pre-planned procedures for which the underlying condition was known and no worsening occurred. An adverse reaction is any untoward and unintended response to an IMP related to any dose administered.

A suspected adverse reaction is any AE for which there is a reasonable possibility that the IMP caused the AE.

Treatment-emergent AEs (TEAEs) are defined as AEs with an onset date on or after the start of IMP treatment during the treatment period. In more detail, TEAEs are defined as all AEs which newly started after the start of IMP treatment during the treatment period; or if the AE was continuous at the start of the treatment period and was worsening.

An SAE includes any event that results in any of the following outcomes:

- Death
- Life-threatening; ie, the subject was, in the opinion of the investigator or subinvestigator, at immediate risk of death from the event as it occurred. It does not include an event that, had it occurred in a more severe form, might have caused death.
- Persistent or significant incapacity/disability or substantial disruption of the ability to conduct normal life functions.

- Requires inpatient hospitalization or prolongs hospitalization.
 - Hospitalization itself should not be reported as an SAE; whenever possible the reason for the hospitalization should be reported.
 - Hospitalizations or prolonged hospitalizations for social admissions (ie, those required for reasons of convenience or other nonmedical need) are not considered SAEs.
 - Prescheduled hospitalization to address a condition that has existed prior to the signing of the ICF should not be considered an SAE.
- Congenital anomaly/birth defect.
- Other medically significant events that, based upon appropriate medical judgment, may jeopardize the subject and may require medical or surgical intervention to prevent one of the outcomes listed above; eg, allergic bronchospasm requiring intensive treatment in an emergency room or home, blood dyscrasias or convulsions that do not result in hospitalization, or the development of drug dependency or drug abuse.

Nonserious AEs are all AEs that do not meet the criteria for a “serious” AE.

Immediately Reportable Event (IRE):

- Any SAE.
- Any AE related to occupational exposure.
- Potential serious hepatotoxicity (see [Section 8.8.6](#)).
- Pregnancies are also defined as immediately reportable events (IREs). Although normal pregnancy is not an AE, it will mandate IMP discontinuation and must be reported on an IRE form and the Pregnancy Surveillance Form(s) to the sponsor. This includes pregnancy of the subject or the partner of the subject. Pregnancy will only be documented on the AE eCRF if the pregnancy occurs in a female subject and there is an abnormality or complication.

Clinical Laboratory Test Value Changes: It is the investigator/subinvestigator’s responsibility to review the results of laboratory tests for each individual subject as they become available. This review will be documented by the investigator/subinvestigator’s dated signature on the laboratory report. The investigator or subinvestigator may repeat the laboratory test or request additional tests to verify the results of the original laboratory tests. However, the central laboratory should not report the results of any repeated or additional tests for fasting lipid assessments, apo B, and hsCRP between Day 1 (Visit T1) and Week 12 (Visit T6) to the trial site and the sponsor to maintain the blind. As for LDL-C and TG, an alert email will be sent from the central laboratory to the investigator, subinvestigator, or their staff if an abnormality exceeding a certain reference value is

observed (details will be specified in a separate procedure). If this laboratory test value is considered medically relevant (ie, clinically significant) by the investigator or subinvestigator (subject is symptomatic, requiring corrective treatment or further evaluation), or if the laboratory test value leads to discontinuation, and/or fulfills a seriousness criterion, this is considered an AE.

Severity: Adverse events will be graded on a 3-point scale below:

- 1 = Mild:** Discomfort noticed, but no disruption to daily activity.
- 2 = Moderate:** Discomfort sufficient to reduce or affect normal daily activity.
- 3 = Severe:** Inability to work or perform normal daily activity.

IMP Causality: Assessment of causal relationship of an AE to the use of the IMP is defined as follows:

- Related:** There is a reasonable possibility of a temporal and causal relationship between the IMP and the AE.
- Not Related:** There is no temporal or causal relationship between the IMP and the AE.

8.8.2 Eliciting and Reporting Adverse Events

The investigator or subinvestigator will regularly assess subjects for the occurrence of AEs. To avoid bias in eliciting AEs, subjects should be asked the nonleading question: “How have you felt since your last visit?” All AEs (serious and nonserious) reported by the subject must be recorded on the source documents and eCRF provided by the sponsor. Adverse event collection will begin after a subject signs the ICF and will continue until the final observation day. All AEs must be recorded in the eCRF after subject informed consent has been obtained, including screening failures due to AEs, irrespective of IMP administration. In this trial, AEs during the screening [REDACTED] [REDACTED] will be assessed compared to Week –5 (Visit S1), and those during the treatment and follow-up periods will be assessed compared to Day 1 (Visit T1).

Medical terminology should be used for AE reporting. Adverse events should be reported as a single unifying diagnosis whenever possible or, in the absence of a unifying diagnosis, as individual signs or symptoms.

Exacerbation or disease progression should be reported as an AE only if there are unusual or severe clinical features that were not present, or experienced earlier, or not expected based on the course of the condition. A reported AE that undergoes worsening in severity or seriousness should be reported as a new AE in the eCRF. However, if worsening of the

condition is observed on Day 1 (Visit 1) or later, the AE should be reported as a new AE in the eCRF without limiting to worsening in severity or seriousness.

In addition, the sponsor must be notified immediately by e-mail in principle of any IREs according to the procedure outlined below, in [Section 8.8.3](#). Special attention should be paid to recording hospitalization and concomitant medications.

The adverse event, start date, end date, seriousness, severity, relationship to trial treatment (IMP causality), action taken with trial treatment, and outcome will be recorded on the source documents and in the eCRF.

8.8.3 Immediately Reportable Events

The investigator/subinvestigator or designee must immediately report (within 24 hours), using forms including an IRE form, after he/she or site personnel become aware of any IRE (SAE, AE related to occupational exposure, potential serious hepatotoxicity, or confirmed pregnancy), by e-mail in principle to the sponsor or designee using the contact information on the cover page of this protocol (please note that the IRE form is NOT the entry column for AEs in the eCRF). Patient confidentiality must be protected and contact information such as name, address, phone number or any other protected health information as determined by applicable local regulation must be redacted when forwarding Safety Information and supporting documentation. Details regarding the follow-up of IREs are included in [Section 8.8.8.2](#).

8.8.4 Medical Device Incidents (Including Malfunctions)

Not applicable.

8.8.5 Adverse Events of Special Interest

Not applicable.

8.8.6 Potential Serious Hepatotoxicity

For a subject who experiences an elevation in AST or ALT that is ≥ 3 times the ULN, a total bilirubin level should also be evaluated. If the total bilirubin is ≥ 2 times the ULN, complete an IRE form or other documentation with all values listed and also report as an AE in the eCRF.

8.8.7 Procedure for Breaking the Blind

When the investigator or subinvestigator determines that emergency code breaking is necessary to ensure the subject's safety in the case of a SAE or other events, the investigator or subinvestigator can obtain the emergency code of the subject from the IWRS in accordance with the separately specified procedure.

The investigator or subinvestigator is encouraged to contact the sponsor/CRO medical advisor to discuss their rationale for unblinding. However, to prevent delays to the investigator/subinvestigator, or medical personnel responding to a potentially emergent situation, unblinding of IMP will not be dependent upon the investigator receiving approval from the sponsor/CRO medical advisor (ie, the investigator or subinvestigator will be able to obtain the code break information independent of the sponsor/CRO medical advisor). The investigator or subinvestigator must contact the sponsor/CRO medical advisor by telephone or e-mail with an explanation of the need for opening the treatment assignment code within 24 hours of opening the code. If the blind is broken, the Global Pharmacovigilance Department must be notified immediately (see the cover page of this protocol for contact information). Documentation of breaking the blind should be recorded in the subject's medical record with the date and time the blind was broken and the names of the personnel involved. Once the blind is broken for a subject, that subject may not reinitiate treatment with the IMP.

8.8.8 Follow-up of Adverse Events

8.8.8.1 Follow-up of Nonserious Adverse Events

Nonserious AEs that are identified at any time during the trial must be recorded on the AE eCRF with the current status (ongoing or resolved/recovered) noted. All nonserious events (that are not IREs) that are ongoing at the last scheduled contact will be recorded as ongoing in the eCRF. For any AE having been identified throughout the trial, during analysis, additional relevant medical history information may be requested by the sponsor to further ascertain causality (including, but not limited to, information such as risk-related behavior, family history, and occupation).

8.8.8.2 Follow-up of Immediately Reportable Events

This trial requires that subjects be actively monitored for IREs up to 28 days after the last dose of IMP is administered.

Immediately reportable events that are **identified or ongoing at the last scheduled contact** must be recorded as such on the AE eCRF page and the IRE form or other documentation. If updated information (eg, resolved status) on IRE status becomes available after a subject's last scheduled contact (up to last in-clinic visit for the entire trial), this must be reported to the sponsor and recorded on the AE eCRF page and the IRE form or other documentation, according to the appropriate reporting procedures described in [Section 8.8.3](#).

It is expected that the investigator or subinvestigator will provide or arrange appropriate supportive care for the subject and will provide prompt updates on the subject's status to the sponsor. The investigator or subinvestigator will follow IREs until the events are:

- Resolved,
- Stabilized,
- The subject is lost to follow-up, or
- Has died.

Resolution means that the subject has returned to the baseline state of health and stabilized means that the investigator or subinvestigator does not expect any further improvement or worsening of the subject's condition. The investigator or subinvestigator will continue to report any significant follow-up information to the sponsor up to the point the event has resolved or stabilized, or the subject is lost to follow-up, or has died.

Refer to [Section 10.3](#) for additional information regarding the duration of follow-up for subjects that become pregnant or for pregnant partners of male subjects.

8.8.3 Follow-up and Reporting of Immediately Reportable Events Occurring After Last Scheduled Contact

Any new IREs reported to the investigator or subinvestigator which occur after the last scheduled contact and are determined by the investigator to be reasonably associated with the use of the IMP, should be reported to the sponsor according to the procedures outlined in [Section 8.8.3](#). This may include IREs that are captured on follow-up telephone contact or at any other time point after the defined trial period and continue to report any significant follow-up information to the sponsor until the events are resolved or stabilized, or the subject is lost to follow-up or has died.

8.9 Treatment of Overdose

For treatment of overdose, refer to the overdose section of the Investigator's Brochure. There is no specific treatment for overdose with ETC-1002. In the event of overdose, symptomatic and supportive therapies should be provided as appropriate.

8.10 Subject Assessment Recording

8.10.1 Completion of Subject Diary

The investigator or subinvestigator will instruct the subjects who are able to receive the IMP to enter the status of compliance with the IMP and hypercholesterolemia drugs, status of diet/exercise therapy and lifestyle (alcohol intake, smoking), presence or absence of subjective symptoms, and the date and time of the IMP administration immediately before the visit in the subject diary and bring it to the visit. The investigator or subinvestigator will record the status of compliance with the IMP and hypercholesterolemia drugs and the date and time of the IMP administration immediately before the visit for blood sampling for pharmacokinetic evaluation in the eCRF based on the contents entered in the subject diary, and also check the status of diet/exercise therapy and lifestyle (alcohol intake, smoking) and changes in subjective symptoms. If any subjective symptom is observed between visits, the investigator or subinvestigator will ask the subject about the symptom, date and time of onset, etc. to determine whether it is an AE.

8.11 Other Assessments

8.11.1 Pregnancy Test

A urine test will be performed for female subjects of childbearing potential according to the schedule specified in [Table 1.3-1](#), and the date and result of the test will be recorded in the source document and the eCRF. A definition of childbearing potential can be found in [Section 10.3](#). [REDACTED] any positive urine test will lead to re-test using serum and the date of blood sampling will be recorded in the source document and the eCRF. The serum test will be performed by the central laboratory selected by the sponsor. Proper sample collection, handling, and shipping procedures will be provided to the trial sites in a separate manual prior to the start of the trial. The central laboratory will report the test results to the investigator or subinvestigator who confirms the test results. The laboratory report will be officially documented by entering the date

of confirmation and signing the report by the investigator or subinvestigator. The results of the serum test will be directly reported to the sponsor by the central laboratory in electronic files. Therefore, it is not necessary to record the results in the source document and the eCRF.

8.11.2 Endocrine Test and Virus Test

Samples for the endocrine test (of TSH) and the virus test (of HBsAg and HCV antibodies) will be collected at Week -5 (Visit S1) to confirm eligibility of subjects regarding thyroid and liver function. The date and time of blood sampling will be recorded in the source document and the eCRF. Samples will be shipped to the central laboratory selected by the sponsor, and eligibility will be confirmed based on the test results measured by the central laboratory. Proper sample collection, handling, and shipping procedures will be provided to the trial sites in a separate manual prior to the start of the trial. The central laboratory will report the test results to the investigator or subinvestigator who confirms the results. The laboratory report will be officially documented by entering the date of confirmation and signing the report by the investigator or subinvestigator. The test results will be directly reported to the sponsor by the central laboratory in electronic files. Therefore, it is not necessary to record the results in the source document and the eCRF.

9 Statistical Considerations

The definitions of the analysis set and the statistical methods for the endpoints in the treatment period are described below. Details of the analysis plan for the treatment period [REDACTED] will be described in the statistical analysis plan (SAP).

9.1 Sample Size

Differences in the percent change in LDL-C from baseline to Week 12 in the ETC-1002 group versus the placebo group in non-Japanese phase 3 trials were -18.1% and -17.42% in trials in statin tolerant subjects and -21.41% and -28.45% in trials in statin intolerant subjects. Base on the results, the difference between the ETC-1002 group and the placebo group in the subjects with statin tolerance was assumed to be 17%, and the difference between the ETC-1002 group and the placebo group in the subjects with statin intolerance was assumed to be 25%. For the present trial it was assumed that the

percentage of statin intolerant subjects enrolled would be 20% and that the difference in the endpoint between the ETC-1002 group and the placebo group would be 19% in the overall trial population. Based on the results of the phase 3 trials, assuming a difference of 19% with standard deviation of 25% between the ETC-1002 groups and the placebo group in the percent change in LDL-C from baseline to Week 12, 38 subjects per group are required to achieve a power of 90% or higher in a two-tailed test with a 5% significance level. Assuming a withdrawal rate of 12.5%, the target number of subjects to be randomized was set at 44 per group.

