1.1 Synopsis

Name of Sponsor:

Otsuka Pharmaceutical Co., Ltd.

Name of Investigational Medicinal Product:

ETC-1002 (Nonproprietary name: Bempedoic acid)

Protocol No.:

346-102-00001

Protocol Title:

A placebo-controlled, randomized, multicenter, double-blind, parallel-group trial to assess the efficacy and safety of ETC-1002 in patients with hypercholesterolemia

Protocol Lay Person Short Title:

A dose-finding trial of ETC-1002 in patients with hypercholesterolemia

Clinical Phase/Trial Type:

Phase 2 trial/Dose-finding trial

Treatment/Indication:

Patients with hypercholesterolemia

Objectives and Endpoints:

Objectives	Endpoints

Primary Objectives:
 
• To assess the low-density lipoprotein cholesterol (LDL-C)-lowering efficacy of ETC-1002 at 60 mg, 120 mg, and 180 mg versus placebo when administered for 12 weeks in combination with ongoing stable statin therapy and/or other lipid-modifying therapy in patients with hypercholesterolemia who have inadequate control of LDL-C• To characterize the dose-response of ETC-1002 and investigate the appropriate dosage for a phase 3 trial	
Primary Endpoint
 
• Percent change in LDL-C from baseline to Week 12

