9.3 Handling of Missing Data for Primary Endpoint Analysis

In the primary analysis of the primary endpoint, when LDL-C at Week 12 is missing, the missing value will be imputed using the last value observed from after initial IMP administration until 2 days after final IMP administration (last observation carried forward: LOCF).

A mixed-effects model repeated measures analysis assuming missing at random will be performed using observed case data as sensitivity analyses.

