9.4.1.4 Control of Experiment-wise Type 1 Error

In the primary analysis of the primary endpoint, type 1 error will be controlled by the comparative test versus the placebo group using a closed testing procedure, starting from the highest dose group.

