3.4 Trial Visit Window

Data observed at CRF Visit will be used at each analysis visit (but data at discontinuation will not be used in analysis). Data from unscheduled visits will not be used. Efficacy analysis will be performed using the data obtained up until 2 days after final IMP administration. In assessment of efficacy endpoints, baseline for fasting lipid parameters is defined as the mean of the values for Day 1 (Visit T1) and Week -1 (Visit S3). If only one value is obtained, that value will be used as baseline. For efficacy endpoints other than fasting lipid parameters, baseline is defined as the value for Day 1 (Visit T1). For safety endpoints, baseline is defined as the last data obtained prior to initial IMP administration in the treatment period.

4 Sample Size

Differences in the percent change in LDL-C from baseline to Week 12 in the ETC-1002 group versus the placebo group in non-Japanese phase 3 trials were -18.1% and -17.42% in trials in statin tolerant subjects and -21.41% and -28.45% in trials in statin intolerant subjects. Based on the results, the difference between the ETC-1002 group and the placebo group in the subjects with statin tolerance was assumed to be 17% , and the difference between the ETC-1002 group and the placebo group in the subjects with statin intolerance was assumed to be 25% . For the present trial it was assumed that the percentage of statin intolerant subjects enrolled would be 20% and that the difference in the endpoint between the ETC-1002 group and the placebo group would be 19% in the overall trial population. Based on the results of the phase 3 trials, assuming a difference of 19% with standard deviation of 25% between the ETC-1002 groups and the placebo group in the percent change in LDL-C from baseline to Week 12, 38 subjects per group are required to achieve a power of 90% or higher in a two-tailed test with a 5% significance level. Assuming a withdrawal rate of 12.5% , the target number of subjects to be randomized was set at 44 per group.

5 Statistical Analysis Datasets

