8.1.1 Primary Efficacy Analysis

For the primary analysis of the primary endpoint, analysis of covariance will be performed using treatment group and statin response (statin tolerance/statin intolerance), the randomization stratification factor, as factors and baseline value of LDL-C as a covariate. The overall Type I error rate will be controlled by performing comparison versus the placebo group starting from the highest ETC-1002 dose group by a closed testing procedure at a two-sided significance level of 0.05. Baseline is defined as the mean of the LDL-C values for Day 1 (Visit T1) and Week -1 (Visit S3). If only one value is observed, that value will be used as baseline. In the analysis of covariance described above, the least squares mean for each treatment group and the differences in the mean of the least squares between each ETC-1002 group and the placebo group, together with the two-sided 95% confidence intervals, will be calculated. The same analysis will also be performed for the percent change in LDL-C from baseline at each visit (Week 2, Week 4, Week 6, Week 8, and Week 12) using measured values (Observed case, OC).

The percent change in LDL-C from baseline to Week 12 will be tested using a contrast for low-dose saturation (L-end), medium-dose saturation (M-end), and linear (L-end: 3-1-1-1, M-end: 5 1-3-3, Linear: 3 1-1-3) to investigate the dose-response relationship between placebo and ETC-1002 low dose, medium dose, and high dose. Multiplicity will not be considered in the analyses for dose-response relationship.

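### Does the 90% power statement mislead because the 120 mg and 60 mg doses are tested in a closed sequence after 180 mg?

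*Protocol*

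**What the plan says.** The sample-size text is the same in the Protocol Synopsis, Protocol 9.1 and SAP Section 4. It uses one effect and one standard deviation, "assuming a difference of 19% with standard deviation of 25% between the ETC-1002 groups and the placebo group", and concludes that "38 subjects per group are required to achieve a power of 90% or higher in a two-tailed test with a 5% significance level". A 12.5% withdrawal rate brings the randomised number to 44 per group.

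Multiplicity is handled separately. Protocol 9.4.1.4 controls type 1 error "using a closed testing procedure, starting from the highest dose group", and SAP 8.1.1 makes the comparisons with placebo "starting from the highest ETC-1002 dose group by a closed testing procedure at a two-sided significance level of 0.05". The order is therefore 180, 120, 60 mg, each step at the full 5% level.

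Three other provisions matter here.

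- The first primary objective covers the "efficacy of ETC-1002 at 60 mg, 120 mg, and 180 mg versus placebo".
- If Week 12 LDL-C is missing, Protocol 9.3 says "the missing value will be imputed using the last value observed".
- SAP 8.1.1 reports least-squares mean differences with 95% confidence intervals for each dose. It also tests contrasts for "low-dose saturation (L-end), medium-dose saturation (M-end), and linear" shapes, without multiplicity adjustment.

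**The concern.** The power statement speaks of the ETC-1002 groups in the plural, and the primary objective names three doses. A reader could take 90% as the chance of claiming each dose. Under the closed sequence it cannot be that: 120 mg needs two rejections and 60 mg needs three, so power falls at each step even when all true effects are equal. Neither document prints a power for the two lower doses.

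The trial exists to choose a phase 3 dose. If 60 mg or 120 mg fails, or is never formally tested, and readers believe each dose had 90% power, they could take the result as evidence of no effect when it may reflect limited power.

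**Working it through.** **Inputs.** Difference 19, SD 25, two-sided 5%, 38 evaluable and 44 randomised per group, 12.5% withdrawal (Protocol 9.1). Allocation is 1:1:1:1 (Protocol 6.3). One ANCOVA across four arms shares the placebo group (SAP 8.1.3).

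**The plan's own figure.** The standard error of a difference is 25 × √(2/n).

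- n = 38: 25 × √(2/38) = 5.735, and 19/5.735 = 3.313. The two-sample t-test has power 90.5%.
- n = 37: power 89.7%, so 38 is the smallest number that reaches 90%.
- Withdrawal: 38/(1 − 0.125) = 43.4, rounded up to 44.

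Both printed numbers reproduce exactly. The 90% is the power of one comparison with placebo, and the 180 mg step is one such comparison at an unadjusted 5%.

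**The sequence with equal effects.** Assume 19 points at every dose. Conditioning on the shared placebo mean, the normal approximation to the probability that the first k steps all reject is

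∫ φ(u) · Φ(√2 · (19/SE − 1.960) − u)^k du.

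At n = 38 the constant is √2 × (3.313 − 1.960) = 1.913. At n = 44, SE = 25 × √(2/44) = 5.330, 19/5.330 = 3.565 and the constant is 2.269. Simulation with t statistics (400,000 replicates; pooled four-arm variance with 4n − 6 degrees of freedom, or pairwise variance) gives nearly the same answers.

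| Analysed per group | Method | 180 mg | 120 mg | 60 mg |
|---|---|---|---|---|
| 38 | normal | 91.2% | 85.1% | 80.4% |
| 38 | t, pooled | 90.9% | 84.7% | 80.1% |
| 38 | t, pairwise | 90.5% | 84.1% | 79.1% |
| 44 | normal | 94.6% | 90.5% | 87.3% |
| 44 | t, pooled | 94.4% | 90.2% | 86.9% |
| 44 | t, pairwise | 94.1% | 89.8% | 86.3% |

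Most of the shortfall comes from needing the earlier rejections. Once a step is reached its power is high: with pooled variance at n = 38, 84.7/90.9 = 93% for 120 mg and 80.1/84.7 = 95% for 60 mg.

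**Which row is nearer the truth.** At the assumed rate, 44 × 0.125 = 5.5 subjects per group withdraw. The full analysis set needs only a baseline and one usable post-dose LDL-C (Protocol 9.2, SAP 5.1), scheduled visits begin at Week 2, and missing Week 12 values are carried forward. The analysed number drops to 38 only if essentially every withdrawn subject leaves no usable value. The rows for 44 are therefore the more relevant.

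**Sensitivity to SD.** The documents do not say whether 25 is adjusted for baseline. With equal effects, the 120/60 mg figures at n = 38 are 92/89% for SD 22.5 and 76/69% for SD 27.5. At n = 44 they are 96/94% and 83/78%. A larger SD lowers the 180 mg step as well. At SD 27.5 and n = 38, SE = 6.309, 19/6.309 = 3.012 and Φ(3.012 − 1.960) is about 85%. That spread belongs to the SD assumption, not to the sequence alone.

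**What is reported whatever the sequence shows.** The confidence-interval half-width for each dose is 1.976 × 5.735 = 11.3 points at n = 38 and 1.974 × 5.330 = 10.5 at n = 44. The code in SAP 8.1.3 produces these intervals and the three contrasts with no condition on an earlier rejection.

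**The case for a change.** The best argument for a change is that it costs only words. The objective names three doses and the sizing sentence uses a plural. On equal effects, the chance of missing the 60 mg claim at the planned 38 is about 20%, twice what 90% suggests. The SAP itself plans contrasts for two shapes in which a lower dose does less. Scale those shapes so that 180 mg gives 19 points. Medium-dose saturation (19, 19, 9.5) then leaves 60 mg with 36% power at n = 38 and 42% at n = 44. The linear shape (19, 12.7, 6.3) leaves 120 mg with 57% to 64% and 60 mg with 16% to 19%. Failure at 60 mg would then be the expected result for an effective drug.

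The arithmetic stands, and so does the point that the plural is loose. The rest is weaker.

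- The sizing sentence claims power for a single two-tailed test. It does not claim 90% per dose or for all doses jointly.
- Equal effects is a fair reading of that plural, but the plan never states it. The preceding sentences use the singular, and Protocol 2.4 ties the non-Japanese efficacy to 180 mg/day.
- The scaled scenarios turn contrast weights into assumed true effects. The SAP uses the weights to test shape, not to size the trial. Most of the loss there is the smaller effect: stand-alone power for 60 mg at n = 38 is already only 38% and 19%. Protocol 2.2 and 4.3, where lower-dose data might appear, cannot be read in the public copy, so these scenarios cannot be judged for realism.
- Nothing in the plan makes dose selection depend on a significant 60 mg test. Dose-response is its own primary objective, with its own contrasts.

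**Conclusion.** No change is needed. The 38, 44 and 90% are correct for one comparison with placebo, and sizing on the 180 mg step of a sequence that starts there is a legitimate choice. The unprinted sequential power, assuming 19 points at every dose and SD 25, is about 85% (38 analysed per group) to 90% (44) for 120 mg, and about 80% to 87% for 60 mg. With carry-forward the upper ends are the likelier ones, so 120 mg roughly meets 90% and 60 mg misses by about 3 points.

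This is an operating characteristic that a statistician can derive from the stated inputs, and no printed figure is wrong. Stating it would move no subject, test, alpha level or estimate. The protection against misreading a failed or unreached lower dose is already planned: an interval for every dose, about 10.5 to 11.3 points either side, plus contrasts that do not depend on the sequence. The conclusion would differ only if the plan claimed 90% for each dose, or tied the phase 3 choice to formal rejection at 60 mg or 120 mg. It does neither.
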